6. DOSING DELAYS/DOSE MODIFICATIONS

Subjects will be evaluated for AEs at each visit with the NCI CTCAE v4.0 used as a guide for the grading of severity. Sections below describe safety run-in and stopping rules, dose reduction steps, instructions for initiation of a new cycle of therapy, and dose modifications during a cycle of therapy.

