6.2 Acalabrutinib

Dose modifications for the following treatment-emergent toxicities are provided in Table 4:

- Grade 4 neutropenia (< 500/µL) for > 7 days
- Grade 3 thrombocytopenia in presence of significant bleeding
- Grade 4 thrombocytopenia
- Grade 3 or 4 nausea, vomiting, or diarrhea, if persistent despite optimal antiemetic and/or anti-diarrheal therapy

- Any other Grade 4 toxicity or unmanageable Grade 3 toxicity

Table 4. Drug Modification Actions for Acalabrutinib

Occurrence	Action
1 st – 2 nd	Hold acalabrutinib until recovery to Grade \leq 1 or baseline; may restart at original dose level
3 rd	Hold acalabrutinib until recovery to Grade \leq 1 or baseline; restart at one dose level lower (100 mg QD)
4 th	Discontinue acalabrutinib

If acalabrutinib is reduced for apparent treatment-related toxicity, the dose need not be re-escalated, even if there is minimal or no toxicity with the reduced dose. However, if the subject tolerates a reduced dose of acalabrutinib for \geq 4 weeks then the dose may be increased to the next higher dose level, at the discretion of the investigator. Such re-escalation may be particularly warranted if further evaluation reveals that the AE that led to the dose reduction was not treatment-related. The maximum dose of acalabrutinib is 100 mg BID.

Treatment with acalabrutinib should be withheld for any unmanageable, potentially study drug-related toxicity that is Grade \geq 3 in severity. Acalabrutinib should be discontinued in the event of an acalabrutinib toxicity lasting more than 28 day. Any other clinically important events where dose delays may be considered appropriate must be discussed with the Principal Investigator.

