6.3.2 Instructions for Lenalidomide Dose Modifications or Interruption

Dose delay and dose reduction rules are as follows and in the table below.

- Lenalidomide dose reduction steps are outlined in Section 6.3.1.
- For treatment interruptions during a cycle, the 28-day schedule of each cycle will continue to be followed. Missed doses of lenalidomide are not made up.
- For treatment interruptions that delay the scheduled start of a new cycle, when toxicity has resolved as required to allow the start of a new cycle (Section 6.5), the restart day of therapy becomes Day 1 of the next cycle when all study medications will restart.

Table 6. Lenalidomide Dose Modifications	
NCI CTC Toxicity Grade	Dose Modification Instructions
Grade 3 neutropenia associated with fever (temperature $\geq 38.5^{\circ}$ C), Grade 4 neutropenia, or Grade 3 neutropenia > 7 days	
 Hold (interrupt) lenalidomide dose. Follow CBC weekly. If neutropenia has resolved to \leq grade 2 prior to Day 21 of the current cycle, restart lenalidomide at next lower dose level and continue through the scheduled Day 21 of the current cycle. Otherwise, omit for remainder of cycle and reduce the dose of lenalidomide by 1 dose level at the start of the next cycle. Omitted doses are not made up. If treatment is delayed for more than 4 weeks, discontinue all protocol therapy and notify the Principal Investigator.
Thrombocytopenia \geqGrade 3 (platelet count $< 50,000/\text{mm}^3$)	
 Hold (interrupt) lenalidomide dose. Follow CBC weekly. If thrombocytopenia resolves to \leq grade 2 prior to Day 21 of the current cycle, restart lenalidomide at next lower dose level and continue through the scheduled Day 21 of the current cycle. Otherwise, omit for remainder of cycle and reduce the dose of lenalidomide by 1 dose level at the start of the next cycle. Omitted doses are not made up.
Platelet count $< 50,000/\text{mm}^3$	
 Hold prophylactic anti-coagulation, if applicable. Restart prophylactic anti-coagulation when platelet count is $\geq 50,000/\text{mm}^3$.

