6.4.1 Neutropenia

For grade 3 or 4 neutrophil count decreased on day 1 of a cycle, delay lenalidomide and acalabrutinib until ANC improves to \leq grade 2, then resume lenalidomide and acalabrutinib with one dose level reduction (Table 7) for all subsequent cycles.

For grade 3 or 4 neutrophil count decreased during a cycle, interrupt lenalidomide and acalabrutinib for the remainder of the cycle. Resume lenalidomide and acalabrutinib (if ANC \leq grade 2) at the next cycle with one dose level reduction (Table 7) for all subsequent cycles.

For febrile neutropenia at any time during a cycle, interrupt or delay lenalidomide and acalabrutinib until toxicity improves to \leq grade 2, then resume lenalidomide and acalabrutinib with one dose level reduction (Table 7) for all subsequent cycles.

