6.4.2 Thrombocytopenia

For grade 3 or 4 platelet count decreased on day 1 of a cycle, delay lenalidomide and acalabrutinib until platelet count improves to \leq grade 2, then resume lenalidomide and acalabrutinib with one dose level reduction (Table 7) for all subsequent cycles.

For grade 3 or 4 platelet count decreased during a cycle, interrupt lenalidomide and acalabrutinib for the remainder of the cycle. If platelets improve to \leq grade 2, then resume lenalidomide and acalabrutinib the next cycle with one dose level reduction (Table 7) for all subsequent cycles.

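### Sections 6.2, 6.3 and 6.4 give incompatible dosing instructions for some cytopenias, and nothing says which section governs

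*Combined protocol and SAP*

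**What the plan says.** Three parts of Section 6 cover neutropenia and thrombocytopenia on the oral drugs.

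- **Section 6.2 (acalabrutinib).** The listed triggers include grade 4 neutropenia beyond 7 days, grade 3 thrombocytopenia with significant bleeding, and "Grade 4 thrombocytopenia". At the first and second occurrence the drug is held until grade ≤ "1 or baseline; may restart at original dose level". The third occurrence brings a step to QD and the fourth brings discontinuation.
- **Section 6.3 (lenalidomide).** Table 6 acts on febrile grade 3 neutropenia, on "Grade 4 neutropenia, or Grade 3 neutropenia > 7 days", and on thrombocytopenia of grade 3 or worse. If the count is back to grade 2 or better before Day 21, the instruction is to "restart lenalidomide at next lower dose level and continue through the scheduled Day 21 of the current cycle". The reduction steps are those of Table 5.
- **Section 6.4 (overlapping toxicities).** For neutrophils, 6.4.1 says "For grade 3 or 4 neutrophil count decreased during a cycle, interrupt lenalidomide and acalabrutinib for the remainder of the cycle". For platelets, 6.4.2 says "For grade 3 or 4 platelet count decreased during a cycle, interrupt lenalidomide and acalabrutinib for the remainder of the cycle". Both drugs resume in the next cycle at grade 2 or better, one Table 7 level lower.

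The opening of Section 6 only lists contents: "Sections below describe safety run-in and stopping rules, dose reduction steps, instructions for initiation of a new cycle of therapy", and mid-cycle modifications. It does not rank the subsections, and neither do 6.2, 6.3, 6.4 or 6.7.

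**The concern.** For some events two instructions apply to the same drug at the same time and point in different directions. In a multicentre trial, sites can then choose differently. The choice decides whether lenalidomide restarts within the cycle and which oral drug is reduced.

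The choice also affects what can be undone. Section 6.3.1 bars lenalidomide re-escalation after a reduction, while 6.2 lets the investigator raise acalabrutinib again after at least 4 weeks on the lower dose.

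Cytopenias are expected. Section 2.2.1 reports grade 3-4 neutropenia in 50% and thrombocytopenia in 13% with frontline lenalidomide-rituximab. Section 2.2.4 reports grade 3-4 neutropenia in 38% with the ibrutinib-based triplet.

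**Working it through.** The plan states no figure to reproduce here, so the check sets the rules side by side and then counts days and doses.

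**1. Same-cycle restart.** Take a mid-cycle event that recovers to grade ≤2 before Day 21.

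| Event | Table 6, lenalidomide | 6.4.1 / 6.4.2, both drugs |
|---|---|---|
| Afebrile grade 4 neutropenia | restart this cycle, one level lower | off until next cycle |
| Afebrile grade 3 neutropenia >7 days | restart this cycle, one level lower | off until next cycle |
| Thrombocytopenia grade ≥3 | restart this cycle, one level lower | off until next cycle |

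Day count for a 6.4 hold from Day d to Day 28: lenalidomide days lost = max(0, 22 − d); acalabrutinib days lost = 29 − d. The onset days below are the scheduled cycle 1 CBC days. The event is grade 4 thrombocytopenia. Recovery to grade ≤1 or baseline by the next weekly CBC is assumed.

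| Found on | Lenalidomide lost: Table 6 / 6.4.2 | Acalabrutinib lost: 6.2 / 6.4.2 |
|---|---|---|
| Day 8 | 7 (Days 8-14) / 22 − 8 = 14 | 7 / 29 − 8 = 21 |
| Day 15 | 7 / 22 − 15 = 7 | 7 / 29 − 15 = 14 |

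For an event found on Day 22, 6.4.2 costs 0 lenalidomide days and 29 − 22 = 7 acalabrutinib days. After cycle 1 the scheduled CBCs fall on Day 1, and weekly CBCs in cycle 2 are optional. This conflict is therefore mainly a cycle 1 matter.

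**2. Dose ladders.**

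| From | Table 5 (lenalidomide) | Table 7 (lenalidomide / acalabrutinib) |
|---|---|---|
| 20 mg, BID | 15, 10, **5** | 15/BID, 10/BID, **10/QD** |
| 15 mg, BID | 10, **5** | 10/BID, **10/QD** |
| 10 mg, BID | **5** | **10/QD** |

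The first reductions from 20 or 15 mg agree. The ladders part at the step down from 10 mg with BID: the third reduction from 20 mg, the second from 15 mg, the first from 10 mg. Per 28-day cycle at that step:

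- Table 5, acalabrutinib still BID under 6.2: 5 × 21 = 105 mg lenalidomide; 200 × 28 = 5,600 mg acalabrutinib.
- Table 7: 10 × 21 = 210 mg lenalidomide; 100 × 28 = 2,800 mg acalabrutinib.

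If the event were also a third occurrence under 6.2, acalabrutinib would be QD on both routes, and only the lenalidomide difference would remain. This conflict can arise in any cycle.

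**3. Acalabrutinib recovery threshold (lesser).** For grade 4 thrombocytopenia, 6.2 requires grade ≤1 or baseline; 6.4.2 resumes at grade ≤2.

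**4. Gaps in Table 7.** Section 5.3.2 starts patients with creatinine clearance 30 to <60 ml/min on lenalidomide 5 mg, with acalabrutinib BID. Table 7 has no such row, so a one-level reduction is undefined for them. Table 7 also ends at 5 mg with QD, while Table 5 has one more step (5 mg every other day) before stopping.

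**Where the rules agree.** For febrile neutropenia, 6.4.1 reads "For febrile neutropenia at any time during a cycle, interrupt or delay lenalidomide and acalabrutinib until toxicity improves to" grade 2 or better, which fits Table 6's same-cycle lenalidomide restart. On Day 1 of a cycle, 6.4 and 6.7 agree on the hold.

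**The case against.** The best defence is that 6.4 is the specific rule and 6.2 and 6.3 are the general ones. Its heading names overlapping toxicities, it addresses both oral drugs together, it has its own ladder, and in conflict 1 it is the longer hold. That is a fair guess at the intent. But no sentence says so, and 6.3.1 makes the toxicities in 6.3.2 the basis for lenalidomide reduction. Every patient starts on both oral drugs, so if 6.4 silently governed, Table 6's same-cycle restart would be a dead letter for the events in conflict 1. Nor does caution settle conflict 2. Taking the lower dose of each drug gives 5 mg with QD, which is two Table 7 levels down when one is ordered. The missing 5 mg/BID row remains even if 6.4 governs.

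Other parts of the defence stand and limit the point:

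- The restart in 6.2 is permissive. A site that holds acalabrutinib to the end of the cycle and to grade ≤1 breaches 6.4.2 only if resumption at grade 2 is compulsory. Hence item 3 is lesser. Section 6.7 is also permissive and is not part of the conflict.
- A reader might infer that the platelet entry minimum of 75,000 makes the baseline alternative in 6.2 irrelevant. The documents do not state the grade 1/2 platelet boundary, and the entry value is a screening requirement that is not defined as baseline.
- A reader might count afebrile grade 3 neutropenia of 7 days or less as a contradiction. It is a difference in triggers: 6.4.1 acts, Table 6 and the listed triggers in 6.2 are silent, and following 6.4.1 breaches neither.
- Item 4 is an omission, not a clash.

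**Conclusion.** The point holds for two contradictions, one lesser difference and one gap. The same-cycle restart in Table 6 cannot be reconciled with the rest-of-cycle hold in 6.4.1 and 6.4.2. From 10 mg with BID, Tables 5 and 7 reduce different drugs: 105 mg and 5,600 mg per cycle against 210 mg and 2,800 mg, assuming BID is kept on the Table 5 route. In the Day 8 example the difference is 7 lenalidomide days and 14 acalabrutinib days, given the assumed recovery date.

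A reader might infer that this distorts the safety run-in. It could, but only under conditions. A 6.4 hold begun by Day 21 of cycle 1 costs more than 7 acalabrutinib days (29 − d > 7), and 6.1 uses that limit both for replacing ALR run-in patients and, as a treatment delay, for excess toxicity. Any reclassification depends on onset and recovery dates and on whether a delay includes a mid-cycle interruption. The choice between replacement and toxicity is an ambiguity within 6.1 itself. The DSMB also decides on all available safety data. A reader might also infer an effect on the response rate after cycle 12; nothing in the documents supports one. The share of patients who would meet these conflicts cannot be computed. This is a matter of treatment conduct and safety, worth correcting.

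**What to change.** State that, while both oral drugs are being given, 6.4.1, 6.4.2 and Table 7 govern the hold, recovery grade, restart timing and dose step for neutropenia and thrombocytopenia, in place of the corresponding hold, restart and reduction instructions in 6.2 and Table 6.

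State also that everything else still applies:

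- in 6.2, the non-cytopenia triggers, discontinuation at the fourth occurrence and the 28-day toxicity limit;
- in Table 6, weekly CBC follow-up, the anticoagulation hold below 50,000 platelets and the rule for delays beyond 4 weeks.

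A blanket statement that 6.4 replaces 6.2 and the cytopenia rows of Table 6 would switch these safeguards off and should be avoided. One merged table that keeps all of these elements would serve equally well.

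In either case, add a Table 7 step for lenalidomide 5 mg with acalabrutinib BID, and a rule for what follows 5 mg with QD.

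Cost: amendment wording and a site memo. No analysis changes.

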6.4.2 Thrombocytopenia

For grade 3 or 4 platelet count decreased on day 1 of a cycle, delay lenalidomide and acalabrutinib until platelet count improves to \leq grade 2, then resume lenalidomide and acalabrutinib with one dose level reduction (Table 7) for all subsequent cycles.

For grade 3 or 4 platelet count decreased during a cycle, interrupt lenalidomide and acalabrutinib for the remainder of the cycle. If platelets improve to \leq grade 2, then resume lenalidomide and acalabrutinib the next cycle with one dose level reduction (Table 7) for all subsequent cycles.

6.4.3 Skin Rash

For grade 3 maculopapular rash, delay (day 1 of a cycle), or interrupt (days 2 through 28 of a cycle) lenalidomide and acalabrutinib until rash improves to \leq grade 1, then resume with one dose level reduction of lenalidomide and acalabrutinib (Table 7) for the current and all subsequent cycles. Discontinue allopurinol if rash is thought to be at least possibly related to allopurinol.

For any rash with sloughing (Stevens-Johnson syndrome, toxic epidermal necrolysis) or Grade 3-4 bullous dermatitis, discontinue all treatment.

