6.3 Lenalidomide

6.3.1 Lenalidomide Dose Modification Steps

Lenalidomide dose will be reduced if patients experience toxicity as defined below in Section 6.3.2. Once the lenalidomide dose has been reduced, no dose re-escalation is permitted. If a new cycle is delayed for more than 4 weeks, remove the patient from protocol therapy. Patients who experience skin rash during cycle 1 which resolves to \leq grade 1 prior to cycle 2 day 1, can restart lenalidomide at the same dose level of cycle 1 without dose escalation.

Table 5. Lenalidomide Dose Levels

	Current Lenalidomide Dose	One Level Dose Reduction
Dose Level +1	20 mg / day	15 mg / day
Dose Level 0	15 mg / day	10 mg / day
Dose Level -1	10 mg / day	5 mg / day
Dose Level -2	5 mg / day	5 mg every other day
Dose Level -3	5 mg every other day*	See below

* Lenalidomide 5 mg every other day on Days 1-21 every 28 days is the minimum lenalidomide dose. Lenalidomide will be discontinued in patients who cannot tolerate this dose.

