Non-blistering rash Grade 3	
 If Grade 3, hold (interrupt) lenalidomide dose. Follow weekly. If the toxicity resolves to \leq grade 1 prior to Day 21 of the current cycle, restart lenalidomide at next lower dose level and continue through the scheduled Day 21 of the current cycle. Otherwise, omit for remainder of cycle and reduce the dose of lenalidomide by 1 dose level at the start of the next cycle. Omitted doses are not made up.
Desquamating (blistering) rash- any Grade	
 Discontinue lenalidomide. Remove patient from study.

Table 6. Lenalidomide Dose Modifications	
NCI CTC Toxicity Grade	Dose Modification Instructions
Neuropathy Grade 3	
 • If Grade 3, hold (interrupt) lenalidomide dose. Follow at least weekly. • If the toxicity resolves to \leq grade 1 prior to Day 21 of the current cycle, restart lenalidomide at next lower dose level and continue through the scheduled Day 21 of the current cycle. Otherwise, omit for remainder of cycle and reduce the dose of lenalidomide by 1 dose level at the start of the next cycle. Omitted doses are not made up.
	
 • If Grade 4, discontinue lenalidomide. Remove patient from study.
Venous thrombosis/embolism \geq Grade 3	
 • Hold (interrupt) lenalidomide and start therapeutic anticoagulation, if appropriate. • Restart lenalidomide at investigator's discretion (maintain dose level). • See Anticoagulation Consideration (Section 8.1.1)
Tumor lysis syndrome \geq Grade 3	
 • Interrupt therapy. • May resume study drug when the TLS resolves to \leq Grade 1 (decrease one dose level)
Tumor Flare \leq Grade 2	
 • at the investigators discretion, may initiate therapy with corticosteroid, NSAIDs and/or Narcotics • Continue Study drug
Tumor Flare Grade 3 or 4	
 • Hold (interrupt) dose and start corticosteroids, NSAIDs and/or Narcotics. • When toxicity resolves to \leq grade 1 restart at next lower dose level

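### The rash instructions in 6.3.1, Table 6 and 6.4.3, and the dose ladders behind them, do not agree and no text says which governs

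*Combined protocol and SAP*

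**What the plan says.** Rash is covered in three places.

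- **Section 6.3.1.** "Patients who experience skin rash during cycle 1 which resolves to" grade 1 or less before cycle 2 day 1 "can restart lenalidomide at the same dose level of cycle 1 without dose escalation". No rash grade is given. The section opens by saying that lenalidomide is reduced for the toxicities set out in 6.3.2.
- **Section 6.3.2, Table 6.** The row "Non-blistering rash Grade 3" holds lenalidomide. If the rash settles to grade 1 or less before day 21, the site is to "restart lenalidomide at next lower dose level and continue through the scheduled Day 21 of the current cycle"; otherwise the next cycle starts one level lower. Acalabrutinib is not mentioned. The row "Desquamating (blistering) rash- any Grade" says "Discontinue lenalidomide. Remove patient from study".
- **Section 6.4.3.** For grade 3 maculopapular rash, both lenalidomide and acalabrutinib are delayed or interrupted until grade 1 or less, "then resume with one dose level reduction of lenalidomide and acalabrutinib (Table 7) for the current and all subsequent cycles". Any rash with sloughing, or "Grade 3-4 bullous dermatitis, discontinue all treatment".

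Table 5 is the dose ladder for lenalidomide alone, and Table 7 is the ladder for the two oral drugs together. The starting lenalidomide dose (5.3.2, Table 3) is 15 mg for creatinine clearance of 60 ml/min or more and 5 mg for 30 to below 60 ml/min.

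**The concern.** Lenalidomide and acalabrutinib are given together throughout induction in both cohorts (5.1.1), so 6.3 and 6.4 apply to the same patient on the same day. If they give different instructions, the outcome depends on which page the site opens. That matters in a multi-institution study, and rash is a toxicity the protocol itself singles out: section 2.2.4 attributes the poor tolerability of the ibrutinib triplet in follicular lymphoma mainly to cutaneous toxicity.

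Three things are at stake: patient safety, exposure to the two oral drugs, and who counts as having stopped for an adverse event. The last feeds the ALO feasibility rule in 11.1, under which no more than 2 of 10 patients may stop treatment in the first year because of adverse events. If two patients have already stopped, how one further rash is handled decides whether that criterion is met.

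**Working it through.** The plan states no figure on this point, so there is none to reproduce. The check is to follow one event through each instruction.

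**Step 1. Restart after a cycle 1 grade 3 maculopapular, non-blistering rash that resolves to grade 1 or less before cycle 2 day 1.**

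| Instruction | Start at 15 mg | Start at 5 mg | Acalabrutinib |
|---|---|---|---|
| 6.3.1 | 15 mg | 5 mg | not mentioned |
| Table 6 with Table 5 | 10 mg | 5 mg every other day | not mentioned |
| 6.4.3 with Table 7 | 10 mg (level 0 to -1) | no level defined | held, then resumed on Table 7 |

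From 15 mg there are three instructions but two lenalidomide doses, 15 mg or 10 mg. Table 6 and 6.4.3 agree on the lenalidomide dose and differ on whether acalabrutinib is held. Section 6.4.3 speaks of reducing both drugs, yet the Table 7 step from level 0 to -1 leaves acalabrutinib at 100 mg BID.

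From 5 mg, 6.4.3 cannot be carried out. Table 7 has no row for 5 mg with 100 mg BID, and nothing lies below its lowest row (5 mg with 100 mg QD).

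**Step 2. The ladders from 10 mg with acalabrutinib 100 mg BID.** This is a later situation, reached after a reduction from 15 mg or an escalation from 5 mg (5.3.2).

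| Ladder | Next lenalidomide dose | Acalabrutinib |
|---|---|---|
| Table 5 | 5 mg per day | not covered |
| Table 7 (level -1 to -2) | 10 mg per day | 100 mg QD |

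The same rash therefore lowers lenalidomide on one ladder and acalabrutinib on the other.

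**Step 3. Blistering rash.**

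| | Table 6 | 6.4.3 |
|---|---|---|
| Trigger | blistering, any grade | sloughing, or bullous dermatitis grade 3-4 |
| What stops | lenalidomide | all treatment |
| Patient status | removed from study | not stated |
| Grade 1-2 blistering, no sloughing | covered | no instruction |

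**Step 4. Precedence.** Section 6.3.1 points to 6.3.2 for reductions, but nothing ranks Table 6 against 6.4.3. The removal criteria in 6.8 do not list blistering rash, so they do not settle the matter.

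**The case against.** The best case for the text is that the sections can be read together.

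- **6.3.1 may not compete with Table 6.** It defers to 6.3.2 in its first sentence, its rash sentence is permissive, and it ends by ruling out escalation. It may only be meant to block the cycle 2 escalation after a rash milder than the Table 6 threshold. That reading is fair. But no grade is stated, so a grade 3 rash falls within the wording, and the cross-reference does not reach 6.4.3.
- **6.4 may be meant to govern overlapping toxicities.** Its title suggests so, but it does not say that it replaces Table 6 when both drugs are given, which is the normal case.
- **Low-grade blistering.** A reader might infer that under 6.4.3 such a patient continues treatment. The section does not say that; it is silent, and a site applying both sections would follow Table 6. What stands is the mismatch in trigger and in stated action.
- **Restart doses.** A reader might infer three different restart doses in the cycle 1 example, or that the 10 mg ladder split belongs to it. Neither holds: from 15 mg there are two lenalidomide doses, acalabrutinib is at 100 mg BID once treatment resumes, and no patient is at 10 mg in cycle 1.
- **Size.** It is tempting to apply the background rash rates to 28 and 10 patients and convert the result into a shift in the primary response rate. The rates are 29% grade 3-4 with lenalidomide-rituximab in untreated mantle cell lymphoma (2.2.1), 14% grade 3-4 and 36% grade 3 with ibrutinib triplets (2.2.4), and 10% grade 3/4 with lenalidomide-obinutuzumab in follicular lymphoma (2.5). None is confined to cycle 1 or separates low-grade blistering, and the restart conflict itself removes nobody. They do not size this problem.

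**Conclusion.** The inconsistency is real and should be corrected. It has three parts: restart instructions that differ on the lenalidomide dose and on holding acalabrutinib; two ladders that diverge from 10 mg, one of which has no step for patients starting at 5 mg; and blistering rules that differ in trigger and in stated action.

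Its size cannot be stated in numbers. The documents give no rate of low-grade blistering or of cycle 1 grade 3 rash with this regimen, so an effect on the primary endpoint is not shown. What is shown is that identical events can be managed and counted differently across sites, including for the ALO 2/10 criterion. The conclusion rests on the current wording and on both oral drugs being given together. It takes no view on which rule or dose is right.

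**What to change.** Reconcile 6.3.1, the two rash rows of Table 6, 6.4.3, and Tables 5 and 7 into one consistent set of instructions for both cohorts. The text should state:

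1. which section governs when both oral drugs are being given;
2. which rash grades the cycle 1 sentence in 6.3.1 covers;
3. whether acalabrutinib is held for rash;
4. which ladder applies on restart, including for patients who start lenalidomide at 5 mg;
5. for blistering and sloughing, by grade, whether lenalidomide or all treatment stops;
6. whether "Discontinue lenalidomide. Remove patient from study" means the end of treatment or of study participation. If it means the end of treatment, say which assessments continue, because the follow-up in 5.6 covers only later therapy and survival and would not supply the cycle 12 response and MRD assessment.

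The sponsor decides which rule and dose stand. The cost is a wording amendment to these sections and tables, with no added visits, procedures or patients.
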